5.3 Vulnerable Subjects

The study will not enroll any vulnerable populations. Children, neonates, and prisoners are not eligible for enrollment. Pregnant women may be included because the intervention poses no physical risk; however no information about pregnancy status will be collected.

5.4 Strategies for Recruitment and Retention

At least 30 men and women with ADHD may be recruited from the community and from local clinical programs through a multimodal outreach program. IRB approval of all recruitment materials will be obtained (via modification as needed) prior to use. Potential participants will contact the study site if interested in participation and will be scheduled for a pre-screen by IRBapproved study personnel.

The pre-screening phone interview will be conducted under a partial waiver of documentation of HIPAA authorization and waiver of documentation of consent. Screening answers will be retained for data analysis (e.g. identify trends in rule-outs) along with identifiers for participants who agree to be re-contacted for future research purposes. The pre-screening phone interview procedures collect the minimum amount of PHI necessary to determine study eligibility. Names, dates, phone numbers, and email are required to determine eligibility, contact participants regarding their eligibility status after consult with study clinicians, and to facilitate re-contact for future research purposes (optional). All data is collected though secure mechanisms, such as phone, WebEx and REDCAP. All data will be stored in restricted drives on the NYULH network and limited to authorized study personnel.

Potential participants will be asked whether they would like their information retained so they can be contacted for future research purposes and whether their information may be retained for analysis. Study personnel administering the pre-screening phone interview consent will document opt-in/opt-out status in a restricted tracking log (either Excel or REDCAP).

- 1. Identifiers from the pre-screen will be destroyed if the participant is not eligible for a screening visit unless the participant authorizes saving their information for contact regarding future research opportunities. They may opt in or opt out of future contact as part of the phone consent. Information collected from participants who opt out of future contact will be destroyed once the pre-screening interview has ended.
- 2. Information collected from participants who opt in to future contact AND who provide verbal HIPAA authorization to allow retention of their data for analysis purposes will be coded with a unique identifier and stored securely.

CONFIDENTIAL

3. Data for eligible participants will be coded with a unique identifier and stored securely as described in the protocol.

All potential participants will be asked questions about basic inclusion and exclusion criteria including medication history, medical history, psychiatric history, potential Attention Deficit Hyperactivity Disorder Symptoms If the participant voluntarily discloses suicidal ideation or intention during the screen, trained study staff will follow the Phone Screen Protocol and Columbia-Suicide Severity Rating Scale and consult with the clinician on-call. Study personnel may ask follow-up questions to clarify responses and assess eligibility. Potential participants who meet minimum eligibility criteria will be invited for a Screening Visit.

Social Media and Online Forums			
	Craigslist		
Online Research Recruitment Sites			
	Research Match		
	StudyKik		
	TrialFacts		
Online Periodicals			
	Time Out Magazine		
	Military Times		
	Schneps Media		
Print Media(cost)			
	Bushwick Daily		
	Queens Chronicle		
Electronic Newsletters /			
	Division of Veteran Services		
	Social Services Agencies		
	Community Mental Health Clinics		
	Community Organizations		
	Local Professional Organizations		
	Regional Employee Assistance Programs		
	Religious Organizations		
	Cultural Centers		
	Social Clubs		
	Local Universities		

CONFIDENTIAL

Medical and Psychiatric	e Clinics		
	Cohen Veteran Center		
	Family Health Centers at NYU Langone and NYU Brooklyn		
	Military Family Clinic at NYUMC		
	Other VA Medical Centers within the greater NYC-area		
	Psychiatry Outpatient Clinic at Bellevue Hospital		
	Primary Care Clinic at Bellevue Hospital		
	Federally Qualified Health Center (FQHC)		
	NYU Lutheran Medical Center Outpatient Psychiatry Clinic		
	Nathan Kline Institute / Rockland Psychiatric Center and		
	Gouverneur Health		
	NYU-Psychiatry Associates		
Clinical Trials (if opted in for Future Contact)			
	Study of the Duration and Efficacy of MYDAYIS on Adult		
	ADHD Symptoms and Executive Function throughout the		
	Day into the Early Evening" IRB# s19-00046 [name]		
	[name] ADHD Trials		

Based on successful recruitment in current and past ADHD trials and the low enrollment goal, we do not expect any significant barriers to recruitment. We expect to recruit the majority of participants from NYULH clinical referrals. If recruitment lags, strategies would include altering staffing patterns and increasing advertisement and outreach to clinical programs as described above.

We expect the study population to be approximately 50% male, 50% female, 7% Hispanic, 60% non-Hispanic Caucasian, 30% Non-Hispanic African American and 3% Other.

5.4.1 Use of DataCore/Epic Information for Recruitment Purposes

The study will utilize EPIC to identify potential participants. DataCore will request a report from EPIC monthly to gather information necessary to identify patients who did not opt out of being contacted for research and who fit eligibility criteria for the study. The PI, co-I, research coordinators, and research nurse practitioners will have access to the EPIC search results. The following data points will be used for the search:

- Ages 18 to 60
- Diagnosis of ADHD
- o Diagnoses of any exclusionary medical conditions or surgeries
- Vision and hearing status

CONFIDENTIAL

• Medications

Once potential participants have been identified, the study team will notify the treating physician (TP) that they have patients eligible to participate and that study team will contact these patients directly by letter, phone, or email. Any recruitment information sent via email will use Send Safe email.

Once contact is made, approved recruitment language will be used to communicate the reason they are being contacted and patients will be asked if they are interested in participating in the study. Should the patient agree, the study team will provide information regarding the next steps for participation. Data will be retained through study completion to ensure that patients who opt out are not contacted multiple times.

If a patient requests information regarding opting out of further recruitment for all research, they will be directed to contact [contact] or [name].

5.5 Duration of Study Participation

Total duration of study participation is 11 weeks. Participants will be assessed for eligibility at the Screening Visit (Week 0) and will be seen for 17 additional visits: Baseline, 15 intervention sessions, and 1 Post-Intervention Visit.

5.6 Total Number of Participants and Sites

Recruitment will end when approximately 30 participants are enrolled. It is expected that approximately 30 participants will be enrolled in order to produce 15 evaluable participants.

5.7 Participant Withdrawal or Termination

5.7.1 Reasons for Withdrawal or Termination

Participants are free to withdraw from participation in the study at any time upon request. An investigator may terminate participation in the study if:

- Any clinical adverse event (AE) or other medical condition or situation occurs such that continued participation in the study would not be in the best interest of the participant.
- The participant meets an exclusion criterion (either newly developed or not previously recognized) that precludes further study participation

5.7.2 Handling of Participant Withdrawals or Termination

Every effort will be made to continue follow-up of withdrawn or terminated participants or participants who discontinue the study intervention but remain in the study for follow-up. If a participant is lost to follow-up, the study team will attempt contact up to 15 times via phone or email to capture adverse events (AEs), serious adverse events (SAEs), and unanticipated problems (Ups). Participants who withdraw or discontinue early will not be replaced.

5.8 Premature Termination or Suspension of Study

This study may be temporarily suspended or prematurely terminated if there is sufficient reasonable cause. Written notification, documenting the reason for study suspension or termination, will be provided by the suspending or terminating party to the investigator, funding agency, and regulatory authorities. If the study is prematurely terminated or suspended, the PI will promptly inform the IRB and will provide the reason(s) for the termination or suspension. Circumstances that may warrant termination or suspension include, but are not limited to:

- Determination of unexpected, significant, or unacceptable risk to participants
- Insufficient compliance to protocol requirements
- Data that are not sufficiently complete and/or evaluable

Study may resume once concerns about safety, protocol compliance, data quality are addressed and satisfy the sponsor and IRB.

6.0 Study Agent (device) and Procedural Intervention

6.1 Study Agent Description

The device to be used in this study (called PRISM) constitutes a non-significant Risk device (see rationale in Section 2.2 above). It is an investigational software under development, intended to be used in research studies testing the clinical efficacy of an innovative paradigm for EEG-based neurofeedback.

Off-the-shelf research-grade EEG hardware (g.Nautilus: Nautilus Research Wearable EEG Headset, wireless 16 electrode cap and amplifier system) will be used in conjunction with the PRISM software.

6.1.1 Acquisition, Labeling, and Storage

EEG hardware was acquired and maintained by NYULH Department of Psychiatry. The investigational (PRISM) software will be provided by Gray Matters, pre-installed on a standard laptop computer. The device is not available for commercial use. All hardware and software will be stored in restricted offices at NYULH Department of Psychiatry.

CONFIDENTIAL

6.1.2 Duration of Intervention

The study will include 15 EEG-NF sessions, administered twice per week for a duration of 8 "active" weeks in total. Twice weekly sessions will be held on non-consecutive days. Each session will last approximately 30 minutes.

6.1.3 Device Specific Considerations

- Device size(s): Not applicable •
- Device model(s): PRISM •
- Device settings and programming: Not applicable ٠
- Duration of implant or exposure: Not applicable •
- Frequency of exposure: Twice weekly for eight weeks ٠

7.0 Study Procedures and Schedule

7.1 Study Procedures/Evaluations

Procedure	Staff	Screening	Baseline	15 x EEG-NF sessions, (2 SESSIONS per week, 8 weeks) Clinical Assessments done once per week	Post-Intervention Visit Week 11
Consent	RA	X			
Demographics	RA	X			
MINI	MD	Х			
ACDS v1.2	MD	Х			
AISRS	MD	Х	X	Х	Х
CGI S	MD	Х	X	Х	Х
Webneuro	Research		X		Х
(CPT/stroop/go-no-go	staff				
included in same					
PTSD battery					
ASRS	Self-	Х	X	X	X
	report				

This material is the property of the NYU School of Medicine and Langone Medical Center. Do not disclose or use except as authorized in writing by the study sponsor Interventional Template Version: 11 January 2019

Page 25

BRIEF A	Self-	Х	Х	Х	Х
	report				
PHQ9	Self-		Х		Х
	report				
PSQI	Self-		Х		Х
	report				
HAM-A	MD		Х		Х
Medical History	MD/RA	Х			
Psychiatric History	MD	Х			
Review Eligibility	MD	Х			
C-SSRS	MD	Х	Х	Х	Х
Prior/Con Meds	MD/RA	Х	Х	Х	Х
Adverse Events	MD/RA	Х	Х	Х	Х
Participant	RA		X	X	X
satisfaction					

7.1.1 Study Specific Procedures

Measures are listed below, organized by domain. The assessment schedule is summarized in the table above.

- 1. Clinical Interview: ADHD diagnosis and severity will be assessed with Adult ADHD Clinical Diagnostic Scale-Version 1.2 (ACDS v1.2), a semi-structured diagnostic interview widely used in adult ADHD studies to evaluate both childhood and adult symptoms of ADHD, the Clinical Global Impression Scale (CGI-S), a widely used clinician-rated measure of global ADHD impairment and severity and Mini International Neuropsychiatric Interview (**MINI**). These measures will be administered by a trained licensed psychologist, nurse practitioner, or MD. Participants will be invited to consent to having their clinical interviews video and/or audio-recorded to ensure clinical adherence and to monitor inter-rater reliability. Discrepancies that result from evaluation of participants will be resolved by group consensus at team meetings.
- 2. Mood, ADHD and Anxiety Symptoms: The Patient Health Questionnaire-9 (**PHQ-9**) will be utilized to objectify degree of depression severity and the Pittsburgh Sleep Quality Index (**PSQI**) will be used to measure participants' quality and patterns of sleep. The Hamilton- A Scale (HAM-A) will be used to assess anxiety symptoms. ADHD symptoms will also be measured using the Adult ADHD Investigator Symptom Rating Scale (AISRS) and the 6-question Attention-Deficit/Hyperactivity Disorder Self-Report Screening Scale for DSM-5 (**DSM-5 ASRS**). Severity of executive function will be assessed via the Behavioral Rating Inventory of Executive Function- Adult version (BRIEF-A) self-report. Suicidality and suicidal ideation will be assessed via the Columbia-Suicide Severity Rating Scale (C-SSRS).

CONFIDENTIAL

- 3. Neurocognitive Testing: Participants will complete a standardized, neuropsychiatric battery through WebNeuro, an abbreviated form of IntegNeuro. WebNeuro is a well-validated, HIPAA-compliant internet-delivered testing battery that probes a wide range of neurocognitive functions. The battery consists of performance-based tests previously validated for remote delivery. Domains include executive functions such as attention/working memory, focus/inhibition, task-shifting, emotion recognition, emotional biasing of attention, and emotion regulation. Data from WebNeuro is linked to the standardized and integrative Brain Resource International database and cognitive functioning domain outputs are computed via WebNeuro software algorithms.
- 4. EFP-EEG-NF training: Each NF training session consists of 5 consecutive sequences of NF presentations. Prior NF session initiated a global BL is performed (3 minutes). Following the global baseline a "watch" condition (60 seconds), in which participants are instructed to passively view the animation, and are told that the scenario is not influenced by their brain activity. In the "regulate" (3 minutes) participants are instructed to lower the room's unrest level. A "rest" phase (30 seconds) follows each sequence, allowing participants to relax.

7.2 Study Schedule

7.2.1 Week 0 - Screening Visit

- Obtain informed consent of potential participant.
- Obtain audio/video consent of potential participant.
- Clinical Interview ACDS v1.2 and MINI
- AISRS
- CGI-S
- C-SSRS
- DSM-5 ASRS (EXPANDED)
- BRIEF-A

7.2.2 Week 1 - Baseline Visit (1 week +/- 5 days)

- AISRS
- CGI-S
- C-SSRS
- ASRS (EXPANDED)
- PHQ9
- PSQI
- HAM-A
- BRIEF- A
- WebNeuro

• Adverse Events

7.2.3 Intermediate Visits (1 week +/- 1 days)

7.2.3.1 Week 2, Visits 1 and 2

- EFP-EEG-NF training
- AISRS
- CGI-S
- C-SSRS
- BRIEF-A
- ASRS (EXPANDED)
- Adverse Events

7.2.3.2 Week 3, Visits 1 and 2 (Clinical Assessments are done once per week)

- EFP-EEG-NF training
- AISRS
- CGI-S
- C-SSRS
- BRIEF-A
- ASRS (EXPANDED)
- Adverse Events

7.2.3.3 Week 4, Visits 1 and 2 (Clinical Assessments are done once per week)

- EFP-EEG-NF training
- AISRS
- CGI-S
- C-SSRS
- BRIEF-A
- ASRS (EXPANDED)
- Adverse Events

7.2.3.4 Week 5, Visits 1 and 2(Clinical Assessments are done once per week)

- EFP-EEG-NF training
- AISRS
- CGI-S
- C-SSRS

CONFIDENTIAL

- BRIEF-A
- ASRS (EXPANDED)
- Adverse Events

7.2.3.5 Week 6, Visits 1 and 2(Clinical Assessments are done once per week)

- EFP-EEG-NF training
- AISRS
- CGI-S
- C-SSRS
- BRIEF-A
- ASRS (EXPANDED)
- Adverse Events

7.2.3.6 Week 7, Visits 1 and 2(Clinical Assessments are done once per week)

- EFP-EEG-NF training
- AISRS
- CGI-S
- C-SSRS
- BRIEF-A
- ASRS (EXPANDED)
- Adverse Events

7.2.3.7 Week 8, Visits 1 and 2(Clinical Assessments are done once per week)

- EFP-EEG-NF training
- AISRS
- CGI-S
- C-SSRS
- BRIEF-A
- ASRS (EXPANDED)
- Adverse Events

7.2.4 Week 9, Final NF Session

- EFP-EEG-NF training
- AISRS
- CGI-S

- C-SSRS
- BRIEF-A
- ASRS (EXPANDED)
- Adverse Events

7.2.5 Week 11 - Final Study Visit (2 weeks +/- 5 days)

- AISRS
- CGI-S
- C-SSRS
- ASRS (EXPANDED)
- BRIEF-A
- PHQ9
- PSQI
- HAM-A
- WebNeuro
- Adverse Events
- Participant Satisfaction

7.2.6 Withdrawal/Early Termination Visit

Participants who are withdrawn or terminated early will be asked to complete a Final Study Visit.

7.2.7 Unscheduled Visit

Unscheduled visits (e.g., in case of unexpected urgent or emergent clinical situation) will be documented on an unscheduled visit form.

7.3 Concomitant Medications, Treatments, and Procedures

All concomitant medications taken during study participation will be recorded on the case report forms (CRFs). Medications to be reported in the CRF are concomitant prescription medications, over-the-counter medications and non-prescription medications. For this protocol, a prescription medication is defined as a medication that can be prescribed only by a properly authorized/licensed clinician.

7.4 Prohibited Medications, Treatments, and Procedures

See Exclusion Criteria.

8 Assessment of Safety

8.1 Specification of Safety Parameters

8.1.1 Definition of Adverse Events (AE)

An *adverse event* (AE) is any symptom, sign, illness or experience that develops or worsens in severity during the course of the study. Intercurrent illnesses or injuries should be regarded as adverse events. Abnormal results of diagnostic procedures are considered to be adverse events if the abnormality:

- results in study withdrawal
- is associated with a serious adverse event
- is associated with clinical signs or symptoms
- leads to additional treatment or to further diagnostic tests
- is considered by the investigator to be of clinical significance

8.1.2 Definition of Serious Adverse Events (SAE)

Adverse events are classified as serious or non-serious. A *serious adverse event* is any AE that is:

- fatal
- life-threatening
- requires or prolongs hospital stay
- results in persistent or significant disability or incapacity
- a congenital anomaly or birth defect
- an important medical event

Important medical events are those that may not be immediately life threatening, but are clearly of major clinical significance. They may jeopardize the subject, and may require intervention to prevent one of the other serious outcomes noted above. For example, drug overdose or abuse, a seizure that did not result in in-patient hospitalization, or intensive treatment of bronchospasm in an emergency department would typically be considered serious.

All adverse events that do not meet any of the criteria for serious should be regarded as *non-serious adverse events*.

8.1.3 Definition of Unanticipated Problems (UP)

Any incident, experience, or outcome that meets all of the following criteria will be documented as an *unanticipated problem (UP) involving risk to subjects or others*:

- Related or possibly related to participation in the research (i.e. possibly related means there is a reasonable possibility that the incident experience, or outcome may have been caused by the procedures involved in the research)
- Suggests that the research places subjects or others at greater risk of harm (including physical, psychological, economic, or social harm).

This definition could include an unanticipated adverse device effect, any serious adverse effect on health or safety or any lifethreatening problem or death caused by, or associated with, a device, if that effect, problem, or death was not previously identified in nature, severity, or degree of incidence in the investigational plan or application (including a supplementary plan or application), or any other unanticipated serious problem associated with a device that relates to the rights, safety, or welfare of subjects (21 CFR 812.3(s)).

8.2 Classification of an Adverse Event

8.2.1 Severity of Event

For AEs not included in the protocol defined grading system, the following guidelines will be used to describe severity.

- Mild Events require minimal or no treatment and do not interfere with the participant's daily activities.
- **Moderate** Events result in a low level of inconvenience or concern with the therapeutic measures. Moderate events may cause some interference with functioning.
- Severe Events interrupt a participant's usual daily activity and may require systemic drug therapy or other treatment. Severe events are usually potentially life-threatening or incapacitating.

8.2.2 Relationship to Study Intervention

The clinician's assessment of an AE's relationship to study agent (drug, biologic, device) is part of the documentation process, but it is not a factor in determining what is or is not reported in the study. If there is any doubt as to whether a clinical observation is an AE, the event should be reported. All AEs must have their relationship to study agent assessed. In a clinical trial, the study product must always be suspect. To help assess, the following guidelines are used.

- **Related or Possibly Related** The AE is known to occur with the study agent, there is a reasonable possibility that the study agent caused the AE, or there is a temporal relationship between the study agent and event. Reasonable possibility means that there is evidence to suggest a causal relationship between the study agent and the AE.
- Not Related There is not a reasonable possibility that the administration of the study agent caused the event, there is no temporal relationship between the study agent and event onset, or an alternate etiology has been established.

8.2.3 Expectedness

The PI will be responsible for determining whether an AE is expected or unexpected. An AE will be considered unexpected if the nature, severity, or frequency of the event is not consistent with the risk information previously described for the study agent.

8.3 Time Period and Frequency for Event Assessment and Follow-Up

The occurrence of an AE or SAE may come to the attention of study personnel during study visits and interviews of a study participant presenting for medical care, or upon review by a study monitor. All AEs including local and systemic reactions not meeting the criteria for SAEs will be captured on the appropriate RF. Information to be collected includes event description, time of onset, clinician's assessment of severity, relationship to study product (assessed only by those with the training and authority to make a diagnosis), and time of resolution/stabilization of the event. All AEs occurring while on study must be documented appropriately regardless of relationship. All AEs will be followed to adequate resolution.

Any medical condition that is present at the time that the participant is screened will be considered as baseline and not reported as an AE. However, if the study participant's condition deteriorates at any time during the study, it will be recorded as an AE. UPs will be recorded in the data collection system throughout the study.

Changes in the severity of an AE will be documented to allow an assessment of the duration of the event at each level of severity to be performed. AEs characterized as intermittent require documentation of onset and duration of each episode.

The PI will record all reportable events with start dates occurring any time after informed consent is obtained until 7 (for nonserious AEs) or 30 days (for SAEs) after the last day of study participation. At each study visit, the investigator will inquire about the occurrence of AE/SAEs since the last visit. Events will be followed for outcome information until resolution or stabilization.

All unresolved adverse events should be followed by the investigator until the events are resolved, the subject is lost to followup, or the adverse event is otherwise explained. At the last scheduled visit, the investigator should instruct each subject to report any subsequent event(s) that the subject, or the subject's personal physician, believes might reasonably be related to participation in this study. The investigator should notify the study sponsor of any death or adverse event occurring at any time after a subject has discontinued or terminated study participation that may reasonably be related to this study. The sponsor should also be notified if the investigator should become aware of the development of cancer or of a congenital anomaly in a subsequently conceived offspring of a subject that has participated in this study.

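### The 7-day and 30-day post-study AE windows have no scheduled inquiry, and the last-visit instruction filters events by believed relatedness before a study clinician sees them

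*Combined protocol and SAP*

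**What the plan says.** - **Window (8.3).** The PI records reportable events from consent "until 7 (for nonserious AEs) or 30 days (for SAEs) after the last day of study participation".
- **Active inquiry (8.3).** "At each study visit, the investigator will inquire about the occurrence of AE/SAEs since the last visit".
- **Schedule (5.5).** "Total duration of study participation is 11 weeks". After screening, participants "will be seen for 17 additional visits: Baseline, 15 intervention sessions, and 1 Post-Intervention Visit". The procedures table (7.1), the visit list (7.2.5) and the payment table (15.3) also end at Week 11.
- **Last-visit instruction (8.3, final paragraph).** Participants are to be told to report later events that they or "the subject's personal physician, believes might reasonably be related to participation in this study".
- **Role of relatedness (8.2.2, 8.3).** The clinician's view of relationship is documented, but "it is not a factor in determining what is or is not reported in the study". Section 8.3 reserves the relationship assessment for staff qualified to make a diagnosis.

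**The concern.** The plan names a recording window but gives no scheduled means of filling it. The instruction that covers the period also hands the first causality judgement to people who are not study clinicians. A participant who has a new serious event after Week 11, and whose physician also attributes it to something else, would follow the instruction correctly by saying nothing.

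Two safety mechanisms depend on events being found. IRB reporting of possibly related SAEs (8.4.2) runs from discovery, and the halting rule (8.5) counts events once discovered. Section 2.2.1 and the text after it say that the method has not been studied in ADHD patients, and 5.2 allows comorbid mood and anxiety disorders that are not the main clinical focus. With about 15 completers, a single missed SAE would change the safety summary. An empty record after Week 11 could be read as 30 days of ascertainment when completers were not asked.

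**Working it through.** The plan gives no figure for coverage of the window, so there is none to reproduce. The check is day arithmetic plus a comparison of the passages.

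**Inputs**
- Consent at Week 0 (7.2.1), taken as day 0.
- Participation of 11 weeks (5.5): 11 × 7 = 77 days. Last visit L = day 77.
- Tolerance of ± 5 days on the final visit (7.2.5): L from 72 to 82.
- Post-study tail T (8.3): 30 days for SAEs, 7 days for nonserious AEs.

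**End of window = L + T**
- SAEs: 77 + 30 = day 107 (72 + 30 = 102 to 82 + 30 = 112).
- Nonserious AEs: 77 + 7 = day 84 (72 + 7 = 79 to 82 + 7 = 89).

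**Share of the recording period after the last scheduled contact = T / (L + T)**
- SAEs: 30/107 = 28% (30/112 = 27% to 30/102 = 29%).
- Nonserious AEs: 7/84 = 8% (7/89 = 8% to 7/79 = 9%).

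The number of scheduled inquiries in either tail is zero.

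**Routes that remain after Week 11, and whether each asks a completer about a new event**
- Follow-up of unresolved AEs (8.3): no, these events are already known.
- Up to 15 contact attempts (5.7.2): no, these are for participants lost to follow-up.
- Final Study Visit for early leavers (7.2.6): nothing is specified after that visit.
- Presentation for medical care, or monitor review (8.3): passive.
- Last-visit instruction (8.3): passive, and limited to events believed related.

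**Passages applied to one case.** Take a hospital admission 20 days after the last visit that the participant and the personal physician both put down to another cause. It starts inside the 30-day window. The instruction does not ask for it. Yet under 8.2.2 a temporal relationship alone can place an event in the related or possibly related class, and 8.3 gives that decision to qualified study staff. As written, they may never receive the event to assess.

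**The case against.** The strongest reply is that the texts do not strictly contradict each other.
- Section 8.2.2 speaks of the clinician's assessment, not of what former participants volunteer.
- The rule in 8.3 that AEs are documented whatever their relationship applies to events on study.
- The window covers reportable events, a term 8.3 does not define. Section 8.4.1 recognises non-reportable AEs, and 8.4.2 sends only possibly related SAEs to the IRB.
- The instruction has no time limit, so it may be an open-ended addition to the window and not its method of ascertainment.

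This stands as a reason to ask for reconciliation rather than to allege a flat contradiction. It does not remove the gap. If the instruction is only an addition, the window has no routine means of ascertainment in completers at all. If reportable means related, relatedness decides what is recorded, which is hard to square with 8.2.2.

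A reader might infer more than the documents support:
- *That contact ceases after Week 11.* It does not. Unresolved AEs are followed, lost participants are pursued and passive routes exist. What is missing is scheduled contact.
- *That only the participant's opinion filters events.* The personal physician's view counts too, and nothing forbids reporting other events.
- *That late harm is expected from the delayed effects in 2.2.1.* Those were improvements in pain and sleep in fibromyalgia.
- *That the gap is larger if counted from the last session.* That re-bases the same 30 days.

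The risk is also limited by design. Sections 5.1 and 5.2 exclude active suicidality in the past year and a suicide attempt in the past 2 years, and require at least 2 months without need of treatment for a comorbid psychiatric condition. The Week 11 visit includes C-SSRS, PHQ9, HAM-A and AE inquiry about two weeks after the last session. The plan calls the device non-significant risk, has a feasibility primary endpoint and claims no 30-day event rate.

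**Conclusion.** The point holds in this form: ascertainment of new-onset events in the 7-day and 30-day windows is passive and filtered by believed relatedness, which fits poorly with 8.2.2 and with the assessor rule in 8.3. It affects 30 of about 107 days for SAEs (28%; 27% to 29%) and all 7 post-study days for nonserious AEs.

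This rests on taking consent as day 0 and the Week 11 visit as the last day of participation. The second is the natural reading of 5.5, but the protocol does not define that day. The percentages describe calendar time. The documents give no basis for estimating how many events would be missed, and the number is probably small. Severity is minor to moderate, given about 15 completers and a device described as non-significant risk.

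**What to change.** Reconcile 8.2.2 with the window and the last-visit instruction in 8.3:

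1. Reword the instruction so that participants report any serious event in the following 30 days, and any new or worse symptom in the following 7 days, whatever they or their physician believe caused it. Study clinicians then judge relationship.
2. Send one short REDCap or email query about 30 days after the last visit, timed for early leavers from their own last visit. REDCap (14.1) and email contact (5.7.2) are already in use.
3. Define the last day of study participation, and say whether reportable events in 8.3 means events of any cause.
4. If no query is sent, state in 8.3 and in the report that events after Week 11 come from spontaneous reporting only.

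The cost is a wording change plus one message and form for about 15 completers and any early leavers. Expect some non-response and a few more events to log. The alternative in step 4 costs one sentence in each document.
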